## **5. PATIENT MANAGEMENT DURING THE CONDUCT OF THE STUDY**

In accordance with a pragmatic study design, patients will receive usual care by their own physician during the conduct of the study. The time between visits, 3-6 months, is in accordance with usual clinical practice and the recommendations of guidelines for regular follow-up of moderate to severe COPD patients.

Other than attending the required number of clinical visits (baseline, and 4 follow-up visits) patients will not be contacted by the research team in relation to this study.

## **6. STUDY TERMINATION AND PATIENT WITHDRAWAL**

### **6.1. Study termination**

There are no formal rules for early termination of this study. During the conduct of the study, serious adverse events will be reviewed as they are reported from the investigational centre to identify safety concerns. The study may be terminated by the sponsor at any time.

### **6.2. Patient withdrawal**

In accordance with the Declaration of Helsinki, each patient is free to withdraw from the study at any time for any reason. The investigator also has the right to withdraw a patient from the study in the event of intercurrent illness, adverse events, or other reasons concerning the health or well-being of the patient, or in case of a protocol deviations.

Should a patient decide to withdraw, all efforts will be made to complete and report all observations up to the time of withdrawal. A complete final evaluation at the time of the patient's withdrawal should be made, and any explanation given by the patient as to why they are withdrawing from the study should be recorded.

The reason for and date of withdrawal from the study must be recorded in the eCRF. If a patient withdraws consent, every attempt will be made to determine the reason. If the reason for withdrawal is an adverse event, monitoring will be continued at the discretion of the investigator (e.g. until the event has resolved or stabilised, until the patient is referred to the care of a health care professional, or until a determination of a cause unrelated to the study drug or study procedure is made). The specific event must be recorded in the eCRF.

## **7. PAYMENTS TO PARTICIPATING CENTRES**

Participating centres will be reimbursed in lieu of incremental cost associated with administration of the study, up to a maximum of ~€100 per patient for the first 50 patients. Payment for additional patients will not be guaranteed, but can be discussed with the Authorised Sponsor Representative on a centre-by-centre basis.

## 8. ADVERSE EVENT REPORTING

No solicited safety data capture is required as this is a prospective study using primary data collection without a drug of interest. However, if during the course of the study participation an adverse event suspected to be associated with the use of a medicinal product is identified in a patient it will be reported to the local Health Authority in accordance with national regulatory requirements or the Marketing Authorization Holder.

The occurrence of adverse events will be sought by non-directive questioning of the patient at each visit during the study. Adverse events also may be detected when they are volunteered by the patient during or between visits or through physical examination, laboratory test, or other assessments.

### 8.1. Definition of Adverse Events

All types of Adverse Events are defined in Table 8, below.

Worsening of the disease during the study will be recorded as an Adverse Event only if the presentation and/or outcome is more severe than would normally be expected from the normal course of the disease in a particular patient.

An exacerbation of COPD is defined as worsening COPD requiring the use of systemic corticosteroids, antibiotics and/or emergency room visit or hospitalisation.

An COPD exacerbation will not be considered an Adverse Event unless it meets the criteria for a serious adverse event. COPD exacerbations that do not meet the criteria for reporting as a serious adverse event will be documented separately from Adverse Events.

Patients with a COPD exacerbation will not be discontinued from the study unless hospitalisation is required, the patient meets any of the stopping criteria in Section 8, or the Principal Investigator believes it is in the patient's best interest to be withdrawn from the study.

Table 8. Definition of adverse events

Adverse Event (AE)	An untoward medical occurrence which does not necessarily have a causal relationship to the IMP or comparator, such as: 
 
 intercurrent illnesses
 
 physical injuries
 
 events possibly related to concomitant medication
 
 significant worsening (change in nature, severity, or frequency) of the disease under study or other pre-existing conditions. (Note: A condition recorded as pre-existing that is intermittently symptomatic [eg, headache] and which occurs during the study should be recorded as an adverse event.)
 

Adverse Drug Reaction (ADR)	An untoward and unintended response to an IMP which has a reasonable causal relationship to the IMP
Unexpected ADR	An ADR whose nature, severity, specificity, or outcome is not consistent with the term or description used in the local/regional product labeling (e.g. Package Insert or Summary of Product Characteristics) should be considered unexpected.
Serious Adverse Event (SAE)	An untoward medical occurrence which does not necessarily have a causal relationship to the IMP or comparator but which: 
 
 results in death
 
 is life threatening
 
 results in persistent or significant disability or incapacity
 
 is a congenital anomaly or birth defect.
 
 is a medically important event or reaction
 

Serious Adverse Reaction (SAR)	An SAE that has a causal relationship to the IMP
Suspected Serious Adverse Reaction (SSAR)	A SAR is consistent with the information about the IMP listed in the Summary of Product Characteristics (SPC).
Suspected Unexpected Serious Adverse Reaction (SUSAR)	A SAR that is suspected to be caused by the IMP but which is not consistent with the information about the IMP in the SPC.

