### **4.3. Outcomes**

#### **4.3.1. Primary outcomes**

The primary study outcome will be measured over the 21-month follow-up period.

The primary outcome of interest will be the difference in (annualized) rates of a composite endpoint (“Mortality, hospitalisations and serious COPD morbidity”) for patients controlled vs uncontrolled at baseline. The composite endpoint is defined as occurrence of any of the following:

- For COPD: unscheduled visits to the physician; emergency room attendance
- An exacerbation of COPD
- All-cause: hospitalization or mortality

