## 9. STATISTICAL ANALYSIS

### 9.1. General

Intention-to-treat and per-protocol analyses will be undertaken. For the Intention-to-treat analysis, all patients entered into the study will be included in the analysis. For the per-protocol analysis, all patients entered who complete the study as per protocol (defined as attending baseline and all follow-up visits irrespective) will be included.

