#### 9.4. Missing data

The per-protocol will not account for missing data as missing data will be seen as a protocol violation and therefore a patient with missing data will be excluded from this population.

The Intent-to-Treat population (ITT) will have missing values imputed as follows:  
Any missing data will be assessed and attempts made to ensure that there are no underlying reasons for the data not being collected. i.e. that the data are missing at random.

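### Hospitalisation for an exacerbation is a primary event and also a stated ground for leaving the study, and the per-protocol set is selected on the outcome

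*Protocol*

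**What the plan says.** **Discontinuation.** Section 8.1 states: "Patients with a COPD exacerbation will not be discontinued from the study unless hospitalisation is required". Two further exceptions follow: meeting stopping criteria said to be in Section 8, and the Principal Investigator's view of the patient's best interest. Section 8 as shown lists no stopping criteria.

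**Primary outcome.** Section 4.3.1 compares the "difference in (annualized) rates of a composite endpoint" between patients controlled and uncontrolled at baseline. The components include "An exacerbation of COPD" and "All-cause: hospitalization or mortality". Section 8.1 defines an exacerbation as "worsening COPD requiring the use of systemic corticosteroids, antibiotics and/or emergency room visit or hospitalisation", so an admitted exacerbation is a primary event. On duration: "The primary study outcome will be measured over the 21-month follow-up period".

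**Follow-up.** Table 7 (Section 4.4.2) records exacerbation and hospitalisation history at Visits 0 to 3. Section 8.2 runs each patient's study period from consent to Visit 3. Section 6.2 seeks observations only up to the time of withdrawal.

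**Analysis sets.** The ITT set in Section 9.1 takes all patients entered. The per-protocol set takes those who complete the study, "defined as attending baseline and all follow-up visits irrespective". Section 9.4 treats missing data as a protocol violation for that set, and "therefore a patient with missing data will be excluded from this population".

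**The concern.** There is no study drug to stop, and patients receive usual care (Section 5), so discontinuation from this study can only mean that observation ends. A COPD admission then both scores as a primary event and opens the way out of follow-up. Once a patient is out, Section 6.2 makes no provision for collecting later exacerbations, admissions or death.

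Three consequences follow.

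- **Censoring depends on the outcome.** It would fall more heavily on uncontrolled patients, because they are expected to have more exacerbations. Sites in five countries may also read a permissive clause differently, so the loss could vary by site.
- **Analyses that count beyond the first event are exposed.** Section 9.3.3 models exacerbation frequency in year 1 (none, one, two or more). A patient discontinued at a first, admitted exacerbation cannot be seen to reach two.
- **The per-protocol set depends on the outcome.** Nobody who dies before the last visit can attend every visit, although death is a primary component. Where the Section 8.1 clause is applied, patients admitted for COPD before the last visit drop out of the set as well.

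**Working it through.** **The plan's own figure.** Section 4.5 allows 15% drop-out: 285 × 1.15 = 327.75, which gives the stated 328. (Dividing by 0.85 gives 335.3, so 336; nothing here turns on that.) The 15% is the allowance that the clause would draw on.

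**Inputs from the protocol.**
- Annual rates λ of 1.2 (taken as uncontrolled) and 0.72 (controlled), true ratio 0.60, true difference 0.48 per year (Section 4.5).
- 55% of patients controlled (Section 4.5).
- Groups assigned at Visit 0, month 3, so T = 21 − 3 = 18 months = 1.5 years.

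**Assumptions, not in the protocol.**
- Every admitted exacerbation leads to discontinuation.
- A share h of exacerbations is admitted: 10–20% in both groups, or 10% controlled against 25% uncontrolled.
- Between-patient heterogeneity follows a gamma distribution with mean 1 and variance (dispersion) d, from 0 to 1.
- Exacerbations stand in for the composite, as in the protocol's own sample size.

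**Formulas.** Let x = hλT.
- Proportion discontinued: 1 − e^(−x) if d = 0; x/(1 + x) if d = 1.
- Pooled rate in all patients (events over person-time): λ if d = 0; λx/[(1 + x) ln(1 + x)] if d = 1.
- Per-protocol rate (patients never admitted): (1 − h)λ/(1 + dx).

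**Worked case: h = 20% in both groups, d = 1.**
- Uncontrolled: x = 0.20 × 1.2 × 1.5 = 0.36. Discontinued 0.36/1.36 = 26.5%. Pooled rate 1.2 × 0.36/(1.36 × 0.3075) = 1.03. Per-protocol rate 0.96/1.36 = 0.706.
- Controlled: x = 0.20 × 0.72 × 1.5 = 0.216. Discontinued 0.216/1.216 = 17.8%. Pooled rate 0.72 × 0.216/(1.216 × 0.1956) = 0.654. Per-protocol rate 0.576/1.216 = 0.474.
- Discontinued overall: 0.45 × 26.5% + 0.55 × 17.8% = 21.7%.
- Rate ratios: 0.654/1.033 = 0.63 pooled; 0.474/0.706 = 0.67 per protocol. Per-protocol difference 0.23 per year.

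The same steps give:

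| Admitted share (controlled / uncontrolled) | d | Discontinued: controlled / uncontrolled / all | Pooled ratio, all patients | Per-protocol ratio | Per-protocol difference per year |
|---|---|---|---|---|---|
| 10% / 10% | 0 | 10% / 16% / 13% | 0.60 | 0.60 | 0.43 |
| 10% / 10% | 1 | 10% / 15% / 12% | 0.62 | 0.64 | 0.33 |
| 20% / 20% | 0 | 19% / 30% / 24% | 0.60 | 0.60 | 0.38 |
| 20% / 20% | 1 | 18% / 26% / 22% | 0.63 | 0.67 | 0.23 |
| 10% / 25% | 0 | 10% / 36% / 22% | 0.60 | 0.72 | 0.25 |
| 10% / 25% | 1 | 10% / 31% / 19% | 0.68 | 0.94 | 0.04 |

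Simulation with 400,000 patients per group agrees with the equal-share rows.

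**The planned group test.** Section 9.3.3 names a Mann-Whitney test, with incidence summarised per person-year. If individual rates are ranked, a patient who leaves at admission keeps that event over a shorter denominator, so that patient's own rate tends to rise. In simulation at d = 1, the probability that an uncontrolled patient has the higher rate (ties counted as half) is 0.593 with full follow-up. It is 0.588–0.591 with equal shares of 10–20%, and 0.603 with 10% against 25%.

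**The case against.** The other side has several good points, and each limits what can be said.

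- **A reader might infer that hospitalised patients must be discontinued.** The text does not say so. It is an exception to a prohibition, Section 6.2 does not list hospitalisation as a reason for withdrawal, and Table 7 and Section 8.2 point to follow-up through Visit 3. What stands is that Section 8.1 is inconsistent with those places. Because investigator judgement is listed as a separate exception, hospitalisation reads as a ground in its own right.
- **A reader might infer that these events remove patients from the analysis altogether.** That is true only of the per-protocol set, which the protocol does not make primary. The ITT set keeps the patient and the triggering event. Time to first composite event is unaffected, since the admission is itself an event.
- **A reader might infer that the contrast between groups must shrink.** The pooled all-patients ratio is unbiased without heterogeneity, and the Mann-Whitney comparison of individual rates hardly moves.
- **A reader might call the per-protocol result meaningless, or the drop-out allowance exhausted.** The 0.94 needs universal discontinuation, strongly unequal admission shares and heterogeneity together. At a 10% admitted share, 12–13% leave by this route, below 15%, although that allowance must cover all other losses too.

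The objection leaves two things untouched. Where the clause is applied, later primary events go uncollected, and no later analysis can recover them. And the per-protocol set excludes deaths before the last visit on any reading.

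**Conclusion.** The point holds as an internal contradiction that should be fixed. Section 8.1 offers a primary event as a ground for ending observation and cites stopping criteria that do not exist. Section 4.3.1, Table 7 and Section 8.2 need observation to continue, and Section 6.2 stops collecting at withdrawal. Separately, Sections 9.1 and 9.4 select the per-protocol set on the outcome.

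Under the assumptions listed, about 12–24% of patients would leave by this route, more of them uncontrolled. The pooled all-patients ratio moves from 0.60 to at most about 0.68. The per-protocol ratio is 0.60–0.72 in most scenarios and about 0.9 only in the extreme one. The per-protocol difference falls from 0.48 to about 0.23–0.43 per year, and lower in that extreme case. The admission shares, the dispersion and full application of the clause are assumptions; the actual loss depends on how sites act. The documents do not support the stronger claim that the main comparison is invalidated.

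**What to change.** Reconcile Sections 4.3.1, 4.4.2 (Table 7), 6.2, 8.1, 8.2, 9.1 and 9.4 as follows.

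1. State that hospitalisation does not by itself end the collection of study outcome data. This concerns data collection only and leaves patient care untouched.
2. Remove the reference to stopping criteria in Section 8, or correct it to where they are.
3. State that outcomes, including later admissions and death taken from clinical records, are collected to month 21 for every patient classified at Visit 0 unless consent is withdrawn.
4. Define the per-protocol set by conditions independent of the outcome: eligibility met and a valid Visit 0 classification. Count death as an event, with follow-up time ending at death.

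The cost is protocol wording plus some record review for patients who stop attending. Clinical records are already a data source for exacerbations (Sections 4.4.1.3 and 9.3.2).

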## 8.2. Recording and reporting adverse events

The study period is defined for each patient as the time period from signature of the informed consent form through to the final follow up visit (visit 3). All adverse events (as defined in Table 8) that occur during the defined study period will be identified, recorded in the eCRF, including the following information:

1. The severity grade (mild, moderate, severe) or (grade 1-4)
2. Its relationship to the drug(s) of interest (suspected/not suspected)
3. Its duration (start and end dates or if continuing at final exam)
4. Whether it constitutes a serious adverse event (SAE)

In addition, all reports of the following special scenarios will be considered an adverse event irrespective of whether a clinical event has occurred:

- Drug-drug or drug-food interaction
- Drug exposure during pregnancy
- Drug use during lactation or breast-feeding,
- Lack of effectiveness
- Overdose
- Drug abuse and misuse
- Drug maladministration or accidental exposure
- Dispensing errors / Medication errors
- Off-label use
- Withdrawal or rebound symptoms

This includes any SAEs likely to arise from the trial indication or progression of underlying/concomitant illness(es) (e.g. progression of cancer in oncology trials), unless specified in the protocol as study specific exemptions.

All serious adverse events (SAEs) will be reported by the Investigator to the Sponsor within 24 hours of the investigator learning that an SAE occurred.

All non-serious AEs will be reported by the Investigator to the Sponsor within 7 days of awareness that the non-serious AE occurred.

Any occurrences of a pregnancy in a patient (or a patients partner) during study participation will be collected. All pregnancies will be followed up to determine outcome, including spontaneous or voluntary termination, details of the birth, and the presence or absence of any birth defects, congenital abnormalities, or maternal and/or newborn complications

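### Hospitalisation is not a seriousness criterion in Table 8, so an admission is an SAE only through another criterion or the investigator's judgement, and some COPD admissions have no reporting deadline

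*Protocol*

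**What the plan says.** Table 8 in Section 8.1 gives five seriousness criteria. An event is an SAE if it "results in death", "is life threatening", "results in persistent or significant disability or incapacity", "is a congenital anomaly or birth defect", or is medically important. Admission to hospital and prolongation of a stay do not appear, and no other section adds them.

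Three rules depend on SAE status:

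- Section 8.1, on exacerbations: "An COPD exacerbation will not be considered an Adverse Event unless it meets the criteria for a serious adverse event". Exacerbations that fall short of this are documented outside AE reporting.
- Section 8.2, on timing: "All serious adverse events (SAEs) will be reported by the Investigator to the Sponsor within 24 hours" of the investigator learning of them. Non-serious AEs follow within 7 days.
- Section 6.1, on oversight during conduct: "serious adverse events will be reviewed as they are reported from the investigational centre to identify safety concerns".

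Elsewhere the protocol gives hospitalisation considerable weight. Section 4.3.1 includes "All-cause: hospitalization or mortality" as a component of the primary composite. Section 8.1 itself makes admission part of the definition of an exacerbation, and one of the conditions under which an exacerbation may lead to discontinuation.

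**The concern.** In a COPD cohort, admission is an obvious marker of a serious event, and the protocol treats it that way everywhere except in the definition that controls safety reporting. For most events, failing the SAE test means a slower report. For an exacerbation it means leaving AE reporting altogether, because the SAE test also decides whether an exacerbation is an AE.

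Two things are at stake. The first is prompt notice: the sponsor review stated for the conduct of the study looks at SAEs as they are reported, so an event not classed as an SAE does not reach it. The second is consistency: SAEs are a listed outcome variable in Section 9.3.2. With about 10 centres in five countries, identical admissions may be classed differently according to how each investigator reads medical importance.

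**Working it through.** No figure in the plan needs reproducing and no calculation decides the point. The check is to apply the rules of Sections 6.1, 8.1 and 8.2 to three kinds of admission.

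| Admission | Status under Section 8.1 | Report to sponsor (8.2) | Review under 6.1 |
|---|---|---|---|
| Any cause; fatal, life threatening, disabling or judged medically important | SAE | 24 hours | Yes |
| Non-COPD; none of the five criteria met | Non-serious AE | 7 days | No |
| COPD exacerbation; none of the five criteria met | Neither SAE nor AE; documented separately | No deadline stated | No |

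Step 1. Admission does not by itself place an event in the first row, because it is not one of the five criteria. One of the five has to apply as well.

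Step 2. Of the five, medical importance is the only one that could take in an ordinary admission that is not fatal, life threatening or disabling. It is a judgement, and Section 8.1 does not say whether admission satisfies it.

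Step 3. The third row gets less prompt reporting than the second. A minor non-COPD AE must reach the sponsor within 7 days, while an exacerbation admission in the third row has no deadline.

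Step 4. Third-row admissions are still recorded. Section 4.4.2 collects history of exacerbations and hospitalisations at visits 0 to 3, held at 3, 9, 15 and 21 months. Those visits are 6 months apart (9 − 3 = 15 − 9 = 21 − 15 = 6), so the endpoint is captured, but this does not replace prompt reporting.

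Step 5. Is this a declared exemption? Section 8.2 brings in SAEs arising from the indication or from progression of underlying illness, unless the protocol specifies study-specific exemptions. Section 8.1 sets aside exacerbations that are not SAEs, but no passage says that admissions are meant to be exempt from SAE status.

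**The case against.** A reader might infer that admissions can never be SAEs, or that they all escape the 24-hour rule. The documents do not support that. The medically important category is open to any investigator, and fatal, life-threatening or disabling admissions qualify without it. Nor do all admissions leave AE reporting: a non-COPD admission judged non-serious is still reported within 7 days and followed up under Section 8.2.1.

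The SAE review is also not the only safety provision. The opening of Section 8 sends AEs suspected to be associated with a medicinal product to the health authority or marketing authorisation holder, with no seriousness threshold. Section 6.1 is, however, the only sponsor review stated for the conduct of the study.

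The strongest objection concerns consequence. The study is non-interventional and has no drug of interest, and Section 8 says solicited safety data are not required. Sections 9.3.3 and 9.3.4 specify no comparison of SAEs between groups, and nothing requires SAE counts to match the hospitalisation component of the composite. All of this stands, and it keeps the point modest. It does not remove it: the protocol chose to define SAEs, to set a 24-hour rule and to base its review on them, and the definition leaves the status of an admission open.

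**Conclusion.** The point holds as an internal mismatch in the safety definitions. Admission alone does not make an event serious. An exacerbation admission that meets none of the five criteria therefore has no reporting deadline and no place in the SAE review, although the protocol counts hospitalisation alongside death in its primary composite.

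Its size cannot be given as a number. Section 4.5 cites 1.2 exacerbations per person per year, and it is tempting to multiply this up to a count of missed admissions. That would need an admission proportion that the protocol does not give. It would also count admissions that are already SAEs through another criterion.

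A reader might also infer that the primary result is compromised. It is not, because hospitalisations are collected at visits 0 to 3 and enter the composite whatever their SAE status. What is affected is the timeliness of sponsor notice and the comparability of SAE counts between centres. The conclusion assumes that the five-item list in Table 8 is complete. It reads as complete, and nothing in the text suggests a lost item. The correction should be made, but nothing in the main analysis depends on it.

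**What to change.** Add to the SAE criteria in Table 8 that an event is serious if it requires inpatient hospitalisation or prolongs an existing hospitalisation. Reconcile the exacerbation paragraphs in Section 8.1 with this, so that they state plainly that an exacerbation leading to admission is an SAE under the 24-hour rule.

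If the sponsor intends admissions already counted in the endpoint to be exempt from SAE reporting, say so as a study-specific exemption, which Section 8.2 allows for. Either route resolves the ambiguity.

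The cost is an amendment of about two lines. The first route also brings more 24-hour SAE forms for events that sites already record. Routine reconciliation of SAE admissions against the hospitalisation component of the composite would be a useful extra but is not needed to correct the definition.
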